 - Peripheral blood immune phenotyping
 - Peripheral blood gene expression profiling
 - Peripheral blood T cell receptor repertoire
 - Peripheral blood serologic responses

Patient Population:

- Sample size: 80 patients; 40 patients in each arm
- Patients with recurrent or persistent endometrial carcinoma or carcinosarcoma, which is refractory to curative therapy or established treatments.
- Patients whose disease has progressed following completion of at least one prior platinum regimen with the following histologic epithelial cell types are eligible:
 - Endometrioid adenocarcinoma
 - Serous adenocarcinoma
 - Undifferentiated carcinoma
 - Mixed epithelial carcinoma
 - Adenocarcinoma not otherwise specified (N.O.S.)
 - Carcinosarcoma
- Adequate organ function and performance status ECOG 0-1
- At least 1 target lesion, which is measurable by RECIST and was not previously irradiated
- Expression of PD-L1 will be assessed from stored tissue samples, but not required for eligibility

Treatment Plan:

Arm 1: Patients will receive intravenous (IV) infusion of durvalumab 1500mg Fixed Dose every 4 weeks until patient develops a loss of clinical benefit or experiences unacceptable toxicities.

Arm 2: Patients will receive durvalumab + tremelimumab combination therapy. Patients will receive 1500 mg Fixed Dose durvalumab via IV infusion q4w for up to 4 cycles and 75 mg tremelimumab via IV infusion q4w for up to 4 cycles, and then continue 1500 mg Fixed Dose durvalumab every 4 weeks until patient develops a loss of clinical benefit or experiences unacceptable toxicities.

Radiologic tumor assessment will be repeated every 8 weeks +/- 7 days for the first 48 weeks and then every 12 weeks +/- 7 days until PD. For patients who remain progression free 2 years post completion of protocol directed treatment, every 6 months +/- 1 month. Treatment will continue until progression, intolerance, withdrawal, study completion, or study

Date:

termination. It is estimated that full accrual will be achieved within 24 months; 3 years is estimated between time of opening and time of last treatment.

Patients will be randomized to either:

- Arm 1: durvalumab (anti-PD-L1 Antibody) alone, or
- Arm 2: durvalumab with tremelimumab (anti-CTLA-4 antibody)

Patients will be stratified by histology, and we will limit enrollment of stratum 1 to 10 patients per arm.

- Stratum 1: endometrial carcinosarcoma patients **OR** MSI-high endometrial carcinoma patients
- Stratum 2: other histologies

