12.5.2 Tissue gene expression profiling and IHC (**MSKCC, [name], [name] lab**)

By using Nanostring nCounter PanCancer Immune Profiling Panel, and immunofluorescence microscopy, archival tumor tissue will be assessed for tumor infiltration with various immune cell subsets, including CD8 cells, CD4+ effector cells (FoxP3-), CD4+ regulatory T cells (FoxP3+), and myeloid cells (CD68+). Tumors will also be assessed for the expression of the known activating co-stimulatory receptors such as 4-1BB (CD137), OX40, GITR, CD40, and ICOS, as well as known immuneinhibitory components such as PD-L1, indoleamine dioxygenase (IDO), B7-H3, B7-H4, LAG3, TIM-3, PD-1, CTLA-4, VISTA, and BTLA. The expression of each gene will be treated as a continuous variable. For exploratory biomarker analyses, patients will be dichotomized on the basis of the primary efficacy endpoint.

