14.0 BIOSTATISTICS

This Phase 2 study aims to assess the activity of Durvalumab alone and in combination with Tremelimumab in patients with recurrent or persistent endometrial carcinomas or endometrial carcinosarcomas. Patients will be randomized to Arm 1: Durvalumab (anti-PD-L1 Antibody) alone or Arm 2: Durvalumab with Tremelimumab (anti-CTLA-4 antibody). This is a randomized study however it is not powered to show superiority of one arm versus another.

In this study, all analyses will be performed by treatment arm.

To date, there are no published studies of immune checkpoint inhibitors in this patient population.

Extrapolating from prior monotherapy studies of immune checkpoint inhibitors in ovarian cancer have yielded overall response rates in the range of 10-15%, and may serve as a basis for historical comparison of the doublet tested here.

Study	N	ORR (CR+PR)	DCR (ORR+SD)	Prior Therapy
Nivolumab (anti-PD-1) 1 mg/kg q 2 weeks (cohort 1) 3 mg/kg q 2 weeks (cohort 2)	10 10	15% (3/20): 10% (1 PR) 20% (2 CR)	50% (5 SD +1 PR) 40% (2 SD +2 CR)	≥ 2 priors Platinum Resistant
Avelumab (anti-PD-L1) Phase Ib expansion cohort 10 mg/kg q 2 weeks	75	10.7% (8 PR)	55% (33 SD +8 PR)	med 4 priors(1-11) Platinum Resistant
Pembrolizumab (anti-PD-1) Phase Ib expansion cohort 10 mg/kg q 2 weeks	26	11.5% (1 CR, 2 PR)	35% (9 SD+1CR+2 PR)	>80% ≥ 4 priors PD-L1+ (IHC)

ORR (defined as CR+PR) will be the primary endpoint. A 10% ORR will be considered low and 25% or higher will be considered promising for further studies. Forty patients provide 90% power and Type I error of 10% using a Simon two stage minimax design. There will be an interim analysis after evaluable 27 patients and if 3 or more responders (CR+PR) are observed out of evaluable 27 patients then the study will continue to the second stage. At the end of the study we require 7 or more responders out of 40 patients to declare this study positive and the arm worthy for further investigation.

Unacceptable response rate: 0.1

Date:

Desirable response rate: 0.25
Error rates: Type I = 0.1 ; Type II = 0.1

# responses required in Stage I	# patients accrued at stage I	# responses required in Stage 2	Total sample size
≥ 3	27	≥ 7	40

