Exploratory objectives: For exploratory biomarker analyses, patients will be dichotomized on the basis of clinical benefit (CBR) rate (CR+PR+SD) as the outcome measure. Exploratory endpoints will be analyzed by treatment arm. All biomarkers without known cutoffs will be treated as continuous variables. For tissue based biomarkers, CBR will be correlated to the level of tissue expression of PD-L1 (binary: positive vs negative), or specific genes/gene signatures identified from transcriptional profiling. Non parametric 2 sample tests will be used to assess differences in the distribution of markers between the 2 groups (responders vs non responders). Archival tumor tissue IHC will be assessed only at baseline while other markers will be assessed at baseline and during treatment and their change from baseline will be analyzed. For markers such as number of infiltrating CD8+ cells and change in ICOS level expression on lymphocytes from baseline levels, we do not have established cutoffs, thus we will examine them as continuous variables. In these biomarkers we will look at changes from baseline to treatment (focused on early changes or changes within 8-12 weeks), and we explore these changes graphically in order to assess potential relationships between responders and non responders.

Date:

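### Biomarkers are tested only within each arm; an added arm-stratified test would use both arms to look for a marker that predicts benefit under either regimen

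*Combined protocol and SAP*

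**What the plan says.** Section 14.0 sets a general rule, "In this study, all analyses will be performed by treatment arm", and repeats it for the biomarkers: "Exploratory endpoints will be analyzed by treatment arm". The test is a nonparametric two-sample comparison of marker values between responders and non-responders. On-treatment changes are also to be explored graphically. The plan describes no combined or arm-stratified biomarker test and no marker-by-arm estimate. It gives no significance level, effect size or power for any biomarker analysis.

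The two places that define the comparison groups disagree. In Section 14.0, "patients will be dichotomized on the basis of clinical benefit (CBR) rate (CR+PR+SD) as the outcome measure". In Section 12.5.2, "For exploratory biomarker analyses, patients will be dichotomized on the basis of the primary efficacy endpoint", and Section 14.0 names ORR as the primary endpoint.

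The group sizes follow from the summary, "Sample size: 80 patients; 40 patients in each arm", and from the ORR design, "A 10% ORR will be considered low and 25% or higher will be considered promising for further studies".

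**The concern.** Section 2.1 words its primary endpoints and its response and clinical-benefit endpoints arm by arm. The exploratory aim is different: it asks whether laboratory parameters predict clinical benefit, with no mention of arm. A plan that tests only within arms uses half of the randomized patients for each answer.

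A marker that predicts under both regimens is plausible from the documents, because both arms receive durvalumab at the same dose and schedule. Two separate small tests of such a marker can easily disagree, and a reader could take the disagreement as evidence of an arm-specific predictor. Two separate p-values also do not estimate how far a marker's association differs between arms. At stake is how well the tissue and blood samples answer the exploratory question. The ORR and PFS decisions are not involved.

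**Working it through.** **1. The plan's own figure.** The 40 per arm comes from the ORR design: "Forty patients provide 90% power and Type I error of 10% using a Simon two stage minimax design". An exact two-stage binomial calculation (at least 3 responders of 27, then at least 7 of 40) gives type I error 0.0977 at 10% ORR and power 0.9001 at 25%. An exhaustive search finds this to be the minimax design, so the stated design reproduces. The plan has no biomarker power figure to reproduce.

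**2. Group sizes.**
- Split by ORR (Section 12.5.2) at the 25% target: 40 × 0.25 = 10 responders and 30 non-responders per arm.
- Split by clinical benefit (Section 14.0): no rate is given for this population. The ovarian table in Section 14.0 prints disease-control rates of 35% to 55%, so 40 × 0.35 = 14 to 40 × 0.55 = 22 per arm. Using these rates here is an assumption. Two entries in that table do not match their own counts (12/26 is 46%, not 35%; 6/10 is 60%, not 50%), so the range is only a guide.

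**3. Power approximation.** Assumptions not in the documents: normal markers, two-sided 5%, a common shift of d SD in both arms, and equal responder numbers per arm. For a rank test of m against n patients,

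λ = d × √(3/π) × √(mn/(m+n)), power ≈ Φ(λ − 1.96).

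With d = 0.8, d × √(3/π) = 0.782.
- One arm, 10 v 30: λ = 0.782 × √7.5 = 2.14, power 57%.
- Two arms stratified: λ = 0.782 × √15 = 3.03, power 86%.

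**4. Simulation check** (20,000 trials per setting). Per arm, the rank sum W of k responders among n patients has mean k(n+1)/2 and variance k(n−k)(n+1)/12; for 10 of 40 these are 205 and 1,025. With equal arms, the stratified statistic is the sum of (W − mean) over arms divided by the square root of the summed variances.

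| Responders per arm | d | One arm | Stratified |
|---|---|---|---|
| 10 | 0.6 | 34% | 60% |
| 10 | 0.8 | 54% | 84% |
| 14–22 | 0.8 | about 63–66% | about 91–92% |

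Repeat runs agree to within about one percentage point. The stratified test's type I error stays near 5% with a 0.5 SD difference in marker level between arms.

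For binary PD-L1, with assumed positivity of 70% in responders and 35% in non-responders, a two-proportion calculation gives 49% power at 10 v 30 and 80% at 20 v 60. With 60% against 35% it gives 28% and 50%.

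**5. A fairer comparator.** The plan tests both arms, so a marker could be found in either (d = 0.8, 10 responders):
- At 5% per arm: 1 − (1 − 0.54)² = 79%, with a false-positive rate of 1 − 0.95² = 9.75%.
- At 2.5% per arm, which holds the overall rate near 5%: 66%.
- Stratified at 5%: 84%.

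**6. Disagreement between arms.** For a shared marker with power p per arm, the chance that exactly one arm is significant is 2p(1 − p): 2 × 0.54 × 0.46 = 50% with 10 responders, and 2 × 0.66 × 0.34 = 45% with 22.

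**7. When the effect is not shared** (d = 0.8, 10 responders). If the marker works in one arm only, power is 54% in that arm and 29% stratified. If the effects are opposite, stratified power is about 3%.

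**8. Marker-by-arm estimate.** The standard error of the difference between the two arms' standardized shifts is about √(2 × (1/10 + 1/30)) = 0.52. The 95% interval is therefore about ±1.0 SD, and power for a 0.8 SD difference is about 34%. It can only be descriptive.

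**The case against.** The best defence is that by-arm analysis is a reasoned choice. The background in Section 3.0 says monotherapy may work better in PD-L1-positive patients, and that adding tremelimumab can raise ORR to 25% in PD-L1-negative NSCLC. PD-L1 might then separate responders less well under the combination. The dose rationale also reports pharmacodynamic activity rising with tremelimumab dose, so on-treatment changes may differ by regimen. This stands as a reason to keep the by-arm tests and to aim the stratified test mainly at baseline markers. It does not justify having no combined test: the same background gives combination response rates of 36% in PD-L1-positive and 25% in PD-L1-negative patients, so the direction is the same under both regimens.

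The analyses are exploratory, with no decision rule, and nothing forbids adding a stratified analysis later. That limits the importance of the point. For a large gene-expression panel, power at an unadjusted 5% is also optimistic under either approach.

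The statement that the trial is not powered for superiority is no defence. The stratified test compares responders with non-responders inside each arm and then combines the results. It does not compare arms.

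A reader might infer more than the documents support:
- *About 10 responders per arm.* This fits only the ORR split at 25%; the clinical-benefit split in Section 14.0 probably gives more.
- *The chance of a miss is halved.* By the approximation in step 3, with 10 responders, the ratio of stratified to one-arm miss rates runs from 0.91 at 0.3 SD to 0.14 at 1.0 SD. Against missing in both arms at 5% each it is 0.98 at 0.5 SD and 0.78 at 0.8 SD.
- *The arms will probably disagree.* Disagreement cannot exceed 50%.
- *All 80 patients will be available.* Eighty is a maximum, since each arm can stop after 27 evaluable patients.

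**Conclusion.** The point holds as a cheap improvement to the exploratory analysis. The plan has no test that uses both arms to look for a marker predicting benefit whichever regimen is given, although its exploratory aim is worded that way. For a shared 0.8 SD marker, a stratified test adds about 26 to 30 percentage points of power over a single arm. With 10 responders per arm it adds 84 − 79 = 5 points over finding the marker in either arm at 5% each, and 84 − 66 = 18 points when each arm is tested at 2.5%.

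These sizes rest on normal markers, equal effects and equal responder numbers in both arms, and full arms of 40. They shrink for weaker markers, and the advantage reverses for an arm-specific one. The documents therefore do not support replacing the by-arm tests, or calling the stratified test free of any trade-off. The conflict over the outcome definition is a plain inconsistency and changes the group sizes. Primary efficacy, safety and go/no-go conclusions are untouched.

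**What to change.** Add one paragraph to the exploratory part of Section 14.0:

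- Beside the by-arm tests, run an arm-stratified test over both arms, mainly for baseline markers: van Elteren for continuous markers and Cochran-Mantel-Haenszel for binary PD-L1.
- State that it assumes a similar effect under both regimens and has less power for a marker that works in one arm only, which is why the by-arm results are still reported.
- Report a marker-by-arm estimate with its confidence interval, labelled descriptive.
- Use one outcome definition in Sections 12.5.2 and 14.0, either the primary efficacy endpoint or clinical benefit.

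The cost is this paragraph and a little programming, with no extra patients, samples or visits. The remaining price is interpretive: one more exploratory result per marker, to be read together with the by-arm results.

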
2.1 OBJECTIVES AND SCIENTIFIC AIMS

Primary Endpoints:

- Determine the effectiveness of the each arm by measuring Overall Response Rate [ORR = Complete Response (CR) + Partial Response (PR)] by RECIST v 1.1
- Determine Progression Free Survival (PFS) rate in each arm at 24 weeks (+/- 1 week)

- **Secondary Endpoints**

- Overall response rate in each arm evaluated by Immune-related Response Criteria in Solid Tumors (irRECIST) criteria. irRECIST assessments will only be completed for patients continuing treatment beyond PD
- Clinical benefit (CR + PR + Stable Disease [SD]) rate in each arm by 24 weeks +/- 7 days Duration of response in each arm
- Determine the rate of immune-related Adverse Events (irAE)
- Determine the rate of serious adverse events (SAE)
- Establish safety of each arm

Exploratory Endpoints:

- Determine the ability of the laboratory parameters to predict clinical benefit:
 - Archival tumor tissue PD-L1 expression IHC
 - Archival tumor tissue immune-related gene expression profiles
 - Archival tumor tissue IHC
 - Peripheral blood immune phenotyping
 - Peripheral blood gene expression profiling
 - Peripheral blood T cell receptor repertoire

Date:

- Peripheral blood serologic responses

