Current experience with single-agent IMT studies suggests that clinical responses may be restricted to a subset of any given patient population and that it might be beneficial to enrich the patient population by selecting patients likely to respond to therapy. To date, no assay has been established or validated, and no single approach has proven accurate, for patient enrichment for IMTs. However, independent data from multiple sources using different assays and scoring methods suggests that PD-L1 expression on tumor cells and/or tumor infiltrating cells may be associated with greater clinical benefit.

Data from ongoing studies with durvalumab and other agents targeting the PD-1/PD-L1 pathway suggest, as shown in a number of tumor types (e.g., NSCLC, renal cell carcinoma, and melanoma), that monotherapy may be more efficacious (in terms of ORR) in patients who are PD-L1-positive.

Date:

Given these findings, a number of ongoing studies are assessing the activity of agents in patients with PD-L1–positive tumors. There is also an unmet medical need in patients with PD-L1–negative tumors that needs to be addressed. Data, as of 27 January 2015 from Study 006 show that with the addition of tremelimumab to durvalumab, the ORR can be increased to 25% in patients with PD-L1 negative NSCLC. As patients with PD-L1 positive disease can also have an increase in ORR, from 25% with durvalumab monotherapy, to 36% with the combination of durvalumab and tremelimumab, the study will enroll all patients with NSCLC, with an emphasis on those determined to be PD-L1 negative.

Potential risks

Potential risks, based on the mechanism of action of durvalumab and related molecules, include immune-mediated reactions, such as colitis, pneumonitis, hepatitis/hepatotoxicity, neuropathy/neuromuscular toxicity, endocrinopathy, dermatitis, pancreatitis and nephritis. Additional important potential risks include infusion related reactions, hypersensitivity, anaphylaxis or serious allergic reactions, serious infections, and immune complex disease.

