12.5.1 Tissue PD-L1 expression (**MedImmune**)

The levels of PD-L1 expression in tumor cells and tumor-infiltrating immune cells will be assessed using SP263 antibody on archival tissue

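### PD-L1 is measured as a level in two cell types but analysed only as positive versus negative, with no cutoff or defining compartment stated; adding the recorded scores is a cheap improvement

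*Combined protocol and SAP*

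**What the plan says.** Section 2.1 lists "Archival tumor tissue PD-L1 expression IHC" first among the exploratory markers. Section 12.5.1 describes the measurement: "The levels of PD-L1 expression in tumor cells and tumor-infiltrating immune cells will be assessed using SP263 antibody on archival tissue". It gives no scoring rule or cutoff, and neither does Appendix D.

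Under the exploratory objectives of Section 14.0:

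- The outcome: "patients will be dichotomized on the basis of clinical benefit (CBR) rate (CR+PR+SD) as the outcome measure".
- The PD-L1 analysis: "CBR will be correlated to the level of tissue expression of PD-L1 (binary: positive vs negative").
- The general rule for markers: "All biomarkers without known cutoffs will be treated as continuous variables".
- The test: "Non parametric 2 sample tests will be used to assess differences in the distribution of markers between the 2 groups".
- The analysis is done within each arm, so on about 40 patients.

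Section 12.5.2 also lists PD-L1 among the components of the archival-tissue panel and treats the expression of each gene as continuous.

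**The concern.** Two graded readouts are collected, and one undefined flag is analysed. Two things follow.

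First, the flag cannot be reproduced from the plan. Section 3.0 reports that in endometrial cancer PD-L1 was seldom seen on tumor cells and was common on intraepithelial immune cells. The choice of compartment therefore largely decides who is positive. Different analysts could form different groups from the same slides, and nothing stops that choice from being made after outcomes are known.

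Second, if benefit rises gradually with PD-L1, cutting the score discards information in a sample that is already small. The stated aim is to learn whether the marker predicts clinical benefit, and the planned analysis could miss a relation that the same slides would show on the measured scale.

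**Working it through.** **Plan's own figures.** The documents give no power, significance level or effect size for the PD-L1 analysis. The only design number used here is 40 per arm, from the two-stage rule (at least 3 of 27, then at least 7 of 40). Summing over first-stage counts k ≥ 3, P(K = k in 27) × P(at least 7 − k in 13), gives 0.0977 at a 10% response rate and 0.9001 at 25%. This matches the stated 10% error and 90% power.

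**Inputs**

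| Input | Value | Source |
|---|---|---|
| Patients per arm | 40 | Section 14.0 |
| With v without benefit | 18 v 22 (45%); alternative 10 v 30 (25%) | Assumed. 45% lies within the 35–55% disease control in the ovarian table of Section 14.0. 25% lies within the 4.2–39.1% 24-week disease control for durvalumab in Section 3.0 |
| Share positive | 39%, 25%, 19.5%, 13% | Assumed. 39% and 13% are the subtype rates in Section 3.0 |
| AUC of the score for benefit | 0.65–0.75 | Assumed |
| Share of scores at zero | 0–75% | Assumed |
| Significance level | two-sided 5% | Assumed |

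The 19.5% comes from the cap of 10 stratum-1 patients per arm. If all 10 were MSI-high, (10 × 0.39 + 30 × 0.13) / 40 = 7.8 / 40 = 19.5%. This assumes that the background rates carry over to SP263 and that no POLE tumors fall in stratum 2.

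**Hand check at a median split.** Take 20 v 20 and a standardized shift d = 0.8.

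- Score, comparing means: Φ(0.8 × √(20/2) − 1.96) = Φ(2.530 − 1.96) = Φ(0.57) = 72%.
- Flag: the shares positive are Φ(0.4) = 65.5% and 34.5%, a difference of 0.311. The standard error is 0.158 under the null and 0.150 under the alternative. Power = Φ((0.311 − 1.96 × 0.158) / 0.150), about 50%.
- The loss is 21 points before rounding. The same formulas give 12 points at d = 0.5, 19 at 0.7 and 1.0, and 13 at 1.2.

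**Simulation, smooth relation.** The score is a latent normal with shift √2 × Φ⁻¹(AUC), floored at zero for the stated share of patients and cut at the top share. The score is tested by Wilcoxon. The flag is tested by uncorrected chi-square and by Fisher. A Wilcoxon test on the flag gives almost the chi-square result (65.2% v 65.6% at 39% positive; 56.0% v 56.2% at 25%), so the chi-square column is the like-for-like comparison.

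| Split | AUC | Positive | Zeros | Score | Flag, chi-square | Flag, Fisher | Like-for-like loss |
|---|---|---|---|---|---|---|---|
| 18 v 22 | 0.75 | 39% | 0–61% | 70–82% | 64–65% | 55–56% | 6–16 |
| 18 v 22 | 0.75 | 19.5% | 0–50% | 73–81% | 53% | 41–42% | 20–28 |
| 18 v 22 | 0.70 | 19.5% | 0–50% | 53–61% | 36–37% | 26–27% | 16–25 |
| 18 v 22 | 0.65 | 19.5% | 0–50% | 32–35% | 21–22% | 14–15% | 10–14 |
| 18 v 22 | 0.75 | 25%, every non-zero positive | 75% | 58% | 56% | 49% | 2 |
| 18 v 22 | 0.75 | 13% | 0–61% | 70–79% | 46–47% | 32% | 23–32 |

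With 10 v 30 and 25–39% positive, the like-for-like loss is 3–13 points at AUC 0.75 and 1–6 at AUC 0.65. Leaving out the extreme 13% cut, the range is therefore about 1 to 28 points. Fisher shows larger losses partly because it is conservative here: its null rejection rate is 1.8–3.8% against a nominal 5%.

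**Simulation, true threshold.** Here benefit depends only on positive v negative at the cut used.

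| Positive | Benefit, positive v negative | Score, Wilcoxon | Flag, Fisher | Flag, chi-square |
|---|---|---|---|---|
| 25% | 80% v 30% | 53% | 73% | 80% |
| 50% | 60% v 30% | 37% | 38% | 49% |

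Across the settings run, the flag gains 1–20 points (Fisher) or 11–27 (chi-square).

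**The case against.** **The power loss is not a document figure.** This stands. AUC, benefit rate, zero share and positivity are all assumed. A reader might infer that the cut typically costs 15 points or more. That holds for a smooth, largely untied score with a moderate effect, or with Fisher's test or a far-from-median cut. It does not hold in general, and under a true threshold the sign changes.

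**The plan does not break its own rule.** A reader might infer that it does, since "All biomarkers without known cutoffs will be treated as continuous variables". But coding PD-L1 as binary presumes that a cutoff is known. Section 3.0 reports durvalumab results by PD-L1-positive and PD-L1-negative status, which fits that presumption. The gap is that the cutoff is not written down.

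**The background does not say that no cutoff exists.** Section 3.0 states "To date, no assay has been established or validated, and no single approach has proven accurate, for patient enrichment for IMTs". That concerns selecting patients, in text carried over from a lung-cancer protocol, and PD-L1 is not an eligibility criterion here.

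**A continuous PD-L1 readout is already planned.** This stands in part. Section 12.5.2 includes PD-L1 in a panel analysed on a continuous scale, but that is not the SP263 score and does not separate the two SP263 compartments.

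**Positive versus negative is a useful format.** This stands. It allows direct comparison with the durvalumab figures in Section 3.0, so demoting it would be a matter of preference.

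**Conclusion.** The point holds as a cheap improvement. The documents collect a PD-L1 level in two compartments, analyse the SP263 result only as a flag, and state neither the cutoff nor the compartment. That omission needs no simulation to establish.

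The cost in power is conditional. For a smooth relation it is roughly 1 to 28 points like for like at 40 per arm. It is near the bottom of that range when most scores are zero, and above it with Fisher's test or about 13% positive. If benefit switches at the cut, the flag is the better analysis. The plan gives no basis for preferring either model, which is the reason to report both forms. The consequence is limited: the analysis is exploratory, carries no power claim, and does not enter the response or progression-free survival rules.

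**What to change.** In the exploratory objectives of Section 14.0:

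1. Add an analysis of the recorded SP263 tumor-cell score and immune-cell score, each as a continuous variable, against clinical benefit, with the nonparametric two-sample test already planned.
2. Keep the positive/negative comparison. Write down its cutoff, its scoring rule and the compartment that defines it (tumor cells, immune cells or both) before outcome data are seen.

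The cost is one extra exploratory comparison per compartment per arm (2 × 2 = 4 in all), and the testing laboratory must transfer scores rather than a flag. No new patient, sample or assay is needed.
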